Pleurodesis is defined as three consecutive drainage attempts with 50cc or less or less than 200cc in 1 week. Patients will be instructed to contact their treatment team who will obtain a CXR to evaluate for resolution of effusion. A CXR showing effusion \leq the size of the effusion at randomization will be considered to be successful pleurodesis. Chest x-ray imaging showing an effusion larger than what was present at randomization (radiographic score 2-5) will be investigated for dysfunction of the pleural catheter. Thoracic ultrasound will be performed at the time of removal of each catheter to assess for presence and size of residual pleural fluid, pleural septations, and for the presence or absence of lung sliding (appendix 1).

Management of Dysfunctional Catheters

Obstructed catheters will be investigated per ASAP I protocol by instillation of 2mg TPA in 8ml sterile water and allowed to dwell for 20 minutes followed by drainage. If the output returns to $>200cc$

after fibrinolytic infusion then patient will return to study protocol. If fibrinolytic fails to produce immediate drainage and the patient does not have shortness of breath the catheter will be removed and the patient will be considered to have undergone partial response. Patients with continued shortness of breath will be managed at the discretion of the treating physician and will be considered catheter failures.

Outcome Measures

Primary Outcome: Percentage of cohort undergoing accelerated pleurodesis. Patients able to have their TPC removed at 30 days post-talc instillation will be considered to have achieved the primary endpoint. Pleurodesis is defined as three consecutive drainage attempts with 50cc or less or less than 200cc in 7 days and lack of respiratory symptoms of cough or shortness of breath previously attributed to pleural effusion. Patients will be considered to have experienced complete (CR) or partial response (PR) depending on chest x-ray (CXR) scoring criteria. Patients who experience pleurodesis later than 30 days from randomization will be considered to have a delayed CR or PR using the same CXR scoring criteria.

Chest X-ray scoring (see appendix 1): Chest x-ray scoring will be performed by a blinded pulmonologist viewing images identified with study code on a CD supplied by the treating physician. Patients with CR will have a CXR score of 0-1, and PR ≥ 2 .

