Secondary Outcomes: Dyspnea and Quality-of-Life Measurements. Baseline Dyspnea measurements will be performed by Visual Analog Scale (VAS), a validated measure of dyspnea in pleural disease. Quality-of-Life measurements will be performed using the short form 36 (SF-36) which is a validated survey-based tool that measures 8 aspects of physical and mental well being. Both of these survey tools will be administered at enrollment, 30, and 90 days after randomization, or at the time of catheter removal if prior to the 30 day or 90 day clinical follow-up. Because patients will be randomized after catheter insertion and drainage for 7 to 14 days, we anticipate dyspnea and QOL to be somewhat optimized as related to interactions from pleural fluid at randomization. The assessments will be examining stability of symptom control over the course of study enrollment.

Adverse Events

Anticipated adverse events include pain with drainage, catheter dislodgement, catheter malplacement, insertion site cellulitis, and empyema. Catheter obstruction due to fibrin will be considered catheter failure, but not an adverse event. There is an extremely small chance of a patient developing local anesthetic systemic toxicity from the instillation of lidocaine mixed with the talc slurry. Intralipid, used to treat this serious complication will be stored in the outpatient procedure suite pyxis.

Selection of Subjects and Data Collection

Diagnosis and Inclusion Criteria:

Subjects must meet all of the following:

1. Male or female, at least 18 years of age, inclusive.
2. Subject has a symptomatic MPE requiring intervention. For an effusion to be defined as malignant, at least one of the following must be true:
 - a. There is histocytological confirmation of pleural malignancy
 - b. The effusion is an exudate (per Light's criteria) in the context of histocytologically proven malignancy elsewhere, with no other clear cause

for fluid identified.

3. Subject has a history of at least 1 ipsilateral pleural effusion causing dyspnea that responded to thoracentesis where the lung expanded and the dyspnea was improved.
4. Subject is willing and able to provide written informed consent.
5. Subject is willing and able to meet all study requirements, including follow-up visits and receiving study-related telephone calls.
6. Subject has sufficient pleural fluid to allow safe insertion of an IPC.
7. Subject has negative pregnancy test if appropriate.

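### Removal of an unresolved blocked catheter is a partial response in one section and possibly a catheter failure in another; the 30-day endpoint needs one counting rule (minor)

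*Combined protocol and SAP*

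**What the plan says.** All references are to the combined protocol and SAP.

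- **Outcome Measures, primary outcome.** The outcome is headed as accelerated pleurodesis, but success is worded as removal: "Patients able to have their TPC removed at 30 days post-talc instillation will be considered to have achieved the primary endpoint". Pleurodesis is defined here by low output and freedom from effusion-related cough or breathlessness. The film then grades the response: "Patients will be considered to have experienced complete (CR) or partial response (PR) depending on chest x-ray (CXR) scoring criteria". A score of 0-1 is complete response and 2 or more is partial response.
- **Criteria for Pleurodesis.** This section uses the same low-output rule and adds a radiographic test. An effusion no larger than "the size of the effusion at randomization will be considered to be successful pleurodesis". A film showing "an effusion larger than what was present at randomization (radiographic score 2-5) will be investigated for dysfunction of the pleural catheter".
- **Management of Dysfunctional Catheters.** There are three branches after fibrinolysis. If output returns to more than 200cc "after fibrinolytic infusion then patient will return to study protocol". If drainage does not return at once and the patient is not short of breath, "the catheter will be removed and the patient will be considered to have undergone partial response". Otherwise, "Patients with continued shortness of breath will be managed at the discretion of the treating physician and will be considered catheter failures".
- **Adverse Events.** "Catheter obstruction due to fibrin will be considered catheter failure, but not an adverse event". No condition is attached on symptoms or on the response to fibrinolysis.

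**The concern.** Take a patient whose catheter is blocked, does not clear, and is removed on day 25 without breathlessness. Under Management of Dysfunctional Catheters this is a partial response, and under the removal wording it is a primary-endpoint success. Under Adverse Events, if the blockage is fibrin, it is a catheter failure. Two analysts following the text could count this patient differently.

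The question the trial asks is about pleurodesis. Low output from a blocked catheter is weak evidence of it, and an effusion that has grown since randomization fails the radiographic test in Criteria for Pleurodesis. Such a patient can still enter the numerator.

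The trial is open-label. The film reader and the statistician are blinded, but neither decides which branch of the obstruction rule applies. The counting rule should therefore be fixed in advance.

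**Working it through.** **1. The same patient under each section** (blocked, not cleared, not breathless, effusion larger than at randomization, catheter removed by day 30)

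| Section | Status |
|---|---|
| Management of Dysfunctional Catheters | Partial response |
| Outcome Measures, removal wording | Endpoint achieved |
| Outcome Measures, pleurodesis definition | Largely met if output was low; cough is not checked |
| Criteria for Pleurodesis | Radiographic test not met |
| Adverse Events, read literally | Catheter failure, if the blockage is fibrin |

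The partial-response label itself agrees with the film: work-up for a larger effusion implies a score of 2-5, and partial response is 2 or more. The disagreement is about whether the patient counts as a success.

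**2. How many patients**

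Inputs from the risk/benefit assessment: about 10% of catheters obstruct, more than 90% of these can be managed, and earlier talc trials noted no excess blockage.

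- Unresolved: 0.10 × 0.10 = 1% of patients.
- Per arm: 0.01 × 92 = 0.92; 0.01 × 101 = 1.01.

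This is approximate, because the protocol does not equate managed with the immediate drainage named in the obstruction rule. With assumed ranges of 8-12% obstructed and 5-20% of these unresolved, it runs from 0.08 × 0.05 = 0.4% (0.37 of 92) to 0.12 × 0.20 = 2.4% (2.21 of 92). The upper end departs from the protocol's own figure of more than 90% managed. Fewer patients reach the disputed rule, since it also requires no breathlessness and, for the primary endpoint, removal by day 30.

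**3. Effect on power**

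Inputs from Power Calculation: 45% vs 65%, one-sided 0.05, 92 per group, 90% power.

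Reproducing the plan's figure first: n = [1.645√(2 × 0.55 × 0.45) + 1.282√(0.45 × 0.55 + 0.65 × 0.35)]² / 0.20² = 104.1, so 105 per arm rather than 92. At 92 per arm:

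power = Φ{[0.20√92 − 1.645√(2 × 0.55 × 0.45)] / √(0.45 × 0.55 + 0.65 × 0.35)} = Φ(1.104) = 86.5%.

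That gap from 90% is a separate matter; 86.5% is used here only as the baseline.

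Suppose the planning rates include these removals (the protocol does not say) and all of the 1% are recounted as not achieved. Then 45%/65% becomes 44%/64%, and the difference stays at 20 points. The Fisher and z-test figures come from exact binomial enumeration at 92 per arm.

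| Method | 45% vs 65% | 44% vs 64% | Change (points) |
|---|---|---|---|
| Fisher | 82.19% | 81.88% | −0.31 |
| Pooled z-test | 85.69% | 85.45% | −0.24 |
| Normal approximation | 86.53% | 86.41% | −0.12 |

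If the planning rates exclude these removals, power is unchanged. With equal true rates, one-sided Fisher rejects in 3.4% of trials at 45% and 3.5% at 44%, so equal recounting in both arms does not inflate false positives.

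**The case against.** The strongest reply is that there is no real contradiction. The sentence in Adverse Events sits among anticipated events, and its evident job is to keep fibrin obstruction off that list. A device can fail while the patient responds, and the specific three-branch rule would ordinarily prevail over a general remark. This is a fair reading and may be the intended one. What remains is that the sentence does not say so, and that the obstruction rule itself uses the same term as the outcome for patients who stay breathless. The obstruction rule also refers to the ASAP I protocol, and the CXR scoring refers to an appendix. Neither is available here, so the partial-response rule may be carried over deliberately.

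Three stronger readings are tempting, and the documents do not support them.

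- **Every fibrin obstruction is an endpoint failure.** This would touch up to about 10% of patients (0.10 × 92 = 9.2 per arm). Scaling both rates by 0.9 gives 40.5% vs 58.5% and takes Fisher power from 82.2% to 73.1%. It requires Adverse Events to override the explicit return of cleared catheters to protocol, all blockage to be fibrin, and all of it to affect the 30-day outcome. It should carry no weight.
- **These patients fail the pleurodesis criteria altogether.** Those who reach work-up through low output and are not breathless largely meet the Outcome Measures definition. They fail the radiographic size test in Criteria for Pleurodesis.
- **The rule favours talc.** The risk/benefit assessment reports no more blockage than baseline with talc, so no direction of bias is shown.

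It can also be said that counting removal without breathlessness as partial response is the plan's stated choice, and that the endpoint and the planning rates are both worded as removal. That stands as an argument for either classification, provided the plan says which one applies.

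**Conclusion.** The point holds as a minor inconsistency. A stated rule can count a non-draining catheter, with a larger effusion than at randomization, as a primary-endpoint success. A second sentence can be read to make the same patient a failure, and the text does not say which governs, nor which of its two descriptions of pleurodesis defines the primary endpoint.

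The expected size is about 1% of patients, roughly one per arm or fewer, with a power change of at most about 0.3 points. This rests on the protocol's own obstruction figures, on managed being close in meaning to cleared, and on similar blockage in both arms. If talc raised blockage in this trial, the effect would be larger and could differ by arm, which is a reason to report obstruction by arm.

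**What to change.** Before outcome data are seen, reconcile Management of Dysfunctional Catheters with Adverse Events:

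1. State one primary-endpoint status for removals due to unresolved obstruction. Endpoint not achieved fits the stated pleurodesis question. Report the other classification as a sensitivity analysis.
2. State that obstructions cleared by fibrinolysis stay in follow-up and are judged by the usual endpoint.
3. If catheter failure in Adverse Events is meant only as an adverse-event label, say so.
4. Say which pleurodesis definition governs the primary endpoint, and refer to it from both sections.
5. Tabulate obstruction, and how it resolved, by arm.

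Only the counting changes; catheter management stays as written. The cost is some wording, one sensitivity analysis and one table, and possibly about 1 point lower counted success per arm if the planning rates include these removals.

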We hypothesize that combining both strategies (daily drainage with the addition of talc sclerosant) will lead to both earlier, and higher incidence of pleurodesis in the majority of treated patients. We believe that this can be achieved on an outpatient basis without additional interactions with the healthcare system.

Design and Procedures

To assess if the addition of talc sclerosant to daily outpatient drainage compared with daily drainage alone leads to more rapid pleurodesis.

Study Type: Non-blinded prospective randomized two-arm cohort

Primary Endpoint: Proportion of cohort able to have TPC removed at 30 days post talc-administration (day of randomization will be defined as study day 1)

Secondary Endpoints: Quality-of-Life Assessment, dyspnea assessment, adverse events

Schedule of Events:

	Screening (up to 14 days prior to baseline visit)	Baseline (Day 0)	30 day follow-up visit	60 day follow-up visit
Tunnel Pleural Catheter insertion (SOC*)	X			
Chest x-ray (SOC)	X		X	X
Physical Exam (SOC)	X	X	X	X
Randomization		X		
Talc instillation (if randomized to Talc Arm) (SOC)		X		
Vital sign monitoring for 2 hours post Talc instillation (if randomized to Talc Arm) (SOC)		X		
SOB VAS questionnaire		X	X	X
SF-36 questionnaire		X	X	X
Daily drainage diary review		X	X	X
AE review		X	X	X

*Standard of Care (SOC) procedures

Enrollment

Patients will undergo TPC insertion for malignant pleural effusion as per usual clinical indications and protocols in either the inpatient or outpatient setting. Patients will be eligible for study enrollment anytime between catheter insertion and initial clinical follow-up at a maximum of 14 days following TPC insertion. Patients will be instructed to drain that catheter daily until initial follow-up. At this 7-14 day follow-up appointment for suture removal patients will be asked to drain the morning of the clinic visit and a chest x-ray (CXR) will be performed prior to the clinic visit. The catheter may be drained at the time of the clinic visit if not done within 8 hours of the visit. Patients who meet radiographic criteria for inclusion (see inclusion/exclusion criteria below) may proceed with randomization via central computer generated randomization table. Those who do not meet radiographic criteria will be considered screen

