failures and withdrawn from the study. At the time of randomization, patients will be given baseline symptom surveys, a drainage diary, and talc instillation or daily drainage alone based on study arm.

Tunneled Pleural Catheter Placement

All patients will have undergone placement of a tunneled pleural catheter prior to consideration for trial enrollment. These are placed utilizing a standard sterile technique under ultrasound guidance. Local Anesthetic will be utilized for placement, which will be performed under sterile conditions on an inpatient or outpatient basis at the discretion of the patient's treatment team. Moderate sedation may be utilized during placement at the treating physicians discretion.

Sclerosant Infusion Procedure

All patients randomized to the Talc arm will receive a slurry composed of 10cc of 1% lidocaine and 4g of graded talc suspended in 50cc of 0.9% saline infused through the pleural catheter. The line will be flushed with a further 10cc of 0.9% normal saline and then de-accessed and dressed in the usual fashion. Control arm patients will not receive any additional therapy. The patients receiving talc will be monitored on-site for 2 hours for the development of dyspnea, followed by drainage of the catheter. Vitals signs will be monitored for stability prior to discharge home. All patients will be instructed to perform drainage daily for the duration of the trial or until catheter removal.

Drainage

All patients will receive drainage bottles after placement and throughout the study to ensure maximum drainage. Patients and their care givers will be instructed on sterile technique for drainage utilizing the tunneled pleural catheters.

Follow up

Study subjects will return for clinic visits at day 30 and 90 after randomization, or a final visit at the time of catheter removal (Figure 1). Review of drainage logs, repeat CXR, SOB VAS and questionnaire, and quality of life measures will be collected at these timepoints. Day 30 and 90 follow up appointments are standard of care for follow up of tunneled pleural catheter management. Additional visits will occur as clinically indicated.

Criteria for Pleurodesis

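### Adverse-event follow-up may end at catheter removal, the event talc is meant to bring forward, and the Follow up text and the Schedule of Events disagree on whether it does

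*Combined protocol and SAP*

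**What the plan says.** Design and Procedures names adverse events among the secondary outcomes: "Secondary Endpoints: Quality-of-Life Assessment, dyspnea assessment, adverse events". The Adverse Events section then lists what is expected: "Anticipated adverse events include pain with drainage, catheter dislodgement, catheter malplacement, insertion site cellulitis, and empyema". It gives no start date, end date or method of comparison, and Data Analysis and Statistics plans no adverse-event analysis.

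On when observation ends, two places differ:

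- The Follow up section says "Study subjects will return for clinic visits at day 30 and 90 after randomization, or a final visit at the time of catheter removal". The Secondary Outcomes paragraph and Follow-up Data Collection use the same either/or for the surveys and the follow-up data.
- The Schedule of Events marks AE review at Baseline, at 30 days and at the "60 day follow-up visit", with no stop at catheter removal.

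The last visit is therefore day 60 in the table and day 90 in the text.

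On when observation starts, the Enrollment section says "Patients will be eligible for study enrollment anytime between catheter insertion and initial clinical follow-up". The Secondary Outcomes paragraph puts randomization 7 to 14 days after insertion. AE review is not marked at Screening.

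Two provisions allow contact outside the scheduled visits. The Follow up section adds "Additional visits will occur as clinically indicated", and inclusion criterion 5 requires willingness to meet study requirements "including follow-up visits and receiving study-related telephone calls".

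**The concern.** Catheter removal by day 30 is the primary outcome, and the trial is powered on talc producing more of it. If removal also closes adverse-event review, the length of safety observation depends on treatment arm and on treatment success. A patient whose catheter comes out in week two would have no further scheduled review, while a patient who keeps the catheter is reviewed to the last visit.

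The Background argues that earlier pleurodesis lowers the risk of long-term complications such as infection. A safety comparison that stops at success cannot tell fewer complications from fewer days of looking. Events that were never asked about after removal cannot be recovered at analysis.

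**Working it through.** The documents give no adverse-event rate or observation time, so there is no stated figure to reproduce. The check asks how far observation would differ if it ended at removal.

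**Inputs from the documents.** Removal rates are 45% (control) and 65% (talc), from Power Calculation, taken at day 30 because that is the primary endpoint. The last visit T is day 60 (Schedule of Events) or day 90 (Follow up).

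**Assumptions.** The mean day of early removal, t, is not stated; I take day 10 to day 30. There are no deaths or dropouts. In the first model, catheters still in place at day 30 stay in until T.

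**Step 1: mean days observed = p × t + (1 − p) × T.** For t = 15 and T = 90:

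- Control: 0.45 × 15 + 0.55 × 90 = 56.25
- Talc: 0.65 × 15 + 0.35 × 90 = 41.25
- Shortfall: 1 − 41.25/56.25 = 27%

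| T | t | Control days | Talc days | Talc shortfall |
|---|---|---|---|---|
| 90 | 10 | 54.0 | 38.0 | 30% |
| 90 | 15 | 56.25 | 41.25 | 27% |
| 90 | 20 | 58.5 | 44.5 | 24% |
| 90 | 30 | 63.0 | 51.0 | 19% |
| 60 | 10 | 37.5 | 27.5 | 27% |
| 60 | 15 | 39.75 | 30.75 | 23% |
| 60 | 30 | 46.5 | 40.5 | 13% |

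**Step 2: allow removals after day 30.** Suppose a share q of the remaining catheters in each arm comes out evenly between day 30 and T. Then T in the formula becomes q(30 + T)/2 + (1 − q)T. Over q = 25% to 50% and t = 15 or 30:

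- The smallest shortfall is 11% (T = 60, q = 50%, t = 30: 42.4 against 37.9 days).
- The largest is 26% (T = 90, q = 25%, t = 15: 52.1 against 38.6 days).

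**Step 3: constant removal hazard.** With h = −ln(1 − p)/30, mean days are (1 − exp(−hT))/h. This gives 35.0 against 25.1 days for T = 60 (28% less) and 41.8 against 27.4 for T = 90 (35% less).

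Across the three models the talc arm is always observed for less time, by roughly 11% to 35%.

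**Step 4: effect on crude proportions.** Take an event that does not depend on the catheter, with equal constant hazard in both arms and an assumed true risk of 10% by day 90, so λ = −ln(0.9)/90. The observed proportion is p(1 − exp(−λt)) + (1 − p)(1 − exp(−λT)).

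| T | t | Control | Talc | Ratio |
|---|---|---|---|---|
| 90 | 15 | 6.3% | 4.6% | 0.74 |
| 90 | 30 | 7.1% | 5.7% | 0.81 |
| 60 | 15 | 4.5% | 3.5% | 0.78 |
| 60 | 30 | 5.3% | 4.6% | 0.87 |

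The true ratio is 1 in every row. The 10% is an illustration, not a figure from the plan.

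**Step 5: dividing by observed time is not a safe repair.** If an early event is equally common in both arms and falls before removal, a rate per day divides equal counts by unequal time. With t = 15 and T = 90, talc would look worse by 56.25/41.25 = 1.36.

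**Step 6: which events are affected.**

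- Pain with drainage and dislodgement cannot occur once the catheter is out, so seeing fewer of them is a real effect of treatment.
- Talc pain and fever are described under Risk/benefit assessment as temporary, and instillation is on the day of randomization, so most should fall before removal.
- Malplacement happens at insertion, before randomization.
- Late empyema, site infection and respiratory events can still occur after removal, and these are the ones that could be missed.

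**The case against.** The strongest reply is that the documents do not plainly stop adverse-event review at removal. The AE review row carries no such stop. The items listed after the Follow up sentence (drainage logs, chest x-ray, dyspnea and quality of life) do not include adverse events. Extra visits are allowed, telephone calls are foreseen, and the interim analysis expects 90-day data. This stands as far as it goes: the plan is in conflict with itself, and it would be wrong to say that it rules out review after removal. But the table does not settle the matter. It has no column for a removal visit, and it marks drainage-diary review at the same visits, which cannot apply once the catheter is out. Visits made when clinically indicated are not systematic ascertainment, least of all in an unblinded trial, and no call schedule is given.

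A reader might also infer three stronger things that the documents do not support:

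- **That the talc arm is watched about a quarter less.** That is one value within the range above. It needs an assumed removal day that the plan does not state.
- **That talc's harm is understated.** No adverse-event analysis is specified, so any bias belongs to whichever analysis is chosen. Acute talc effects mostly precede removal, and catheter-bound events cannot follow it. Respiratory failure is put at about 1 in 10,000, so with 101 talc patients about 0.01 cases would be expected.
- **That events before randomization favor talc.** Of the listed events only malplacement must predate allocation; insertion-site cellulitis can arise later. Earlier events are balanced in expectation by randomization. They add noise but not direction.

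**Conclusion.** The concern holds in a limited form. The Follow up section, taken as written, lets scheduled contact for a secondary endpoint end at the primary-endpoint event, and the Schedule of Events contradicts it. On that reading, observation in the talc arm is shorter by roughly 11% to 35%. This rests on the planning removal rates, the assumed removal times, a last visit at day 60 or day 90, and no deaths or dropouts. A crude comparison could then under-count talc-arm events that can still occur after removal; in the equal-hazard illustration a true ratio of 1 appears as 0.74 to 0.87. The size and direction of any bias depend on the type of event and on the analysis. Inclusion of insertion events is a minor, non-directional matter.

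**What to change.** 1. Reconcile the day 60 visit in the Schedule of Events with the day 90 visit in the text.
2. State that adverse events are collected from randomization to that one fixed day in every patient, whatever the catheter status. For patients whose catheter is out, use the study telephone calls already anticipated in inclusion criterion 5.
3. Compare the arms only on events with onset after randomization, over fixed windows: to day 30, and from day 31 to the last visit.
4. List events between insertion and randomization, such as malplacement, separately as baseline.

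Planned observation then becomes equal, 60 against 60 or 90 against 90 days, apart from death and dropout.

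The cost is a paragraph in the protocol and one or two short calls for each patient with early removal. At the planning rates that is 0.65 × 101 + 0.45 × 101 = 111 patients, plus any whose catheter comes out between day 30 and the last visit.

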Data to be collected at the time of enrollment include age, sex, race, ethnicity, effusion side, type of malignancy, date of diagnosis, date of initial thoracentesis, Karnofsky performance score, ECOG performance score, comorbidities (anemia, asthma, cerebrovascular accident, chronic kidney disease, chronic obstructive pulmonary disease, coagulopathy, congestive heart failure, coronary artery disease, diabetes, deep vein thrombosis, pulmonary embolism, hypertension, hypothyroidism, hyperthyroidism, interstitial lung disease, nephrotic syndrome, peripheral vascular disease, cirrhosis of the liver), pleural fluid characteristics (pH, LDH, Protein, % lymphocytes, glucose, cytology results), prior chemotherapy, prior radiotherapy, prior immunomodulatory therapy, VAS dyspnea score, and SF-36 questionnaire. Data collected at randomization will be CXR score by treating and blinded physician.

Follow-up Data Collection

Karnofsky score, ECOG score, VAS dyspnea score, SF-36 questionnaire, and CXR scoring will be collected at the 30 day and 90 day clinic visits, or at the time of catheter removal. Thoracic ultrasound examination will be performed at time of catheter removal.

Subject Recruitment and Compensation

Consent Process- Consent form and material subject to IRB approval

Risk/benefit assessment- There are two primary risks to patients associated with this study. The first is the risk of respiratory failure associated with talc pleurodesis. Respiratory failure is a rare but well documented risk associated with the use of talc for pleurodesis. This event is rarely fatal and occurs roughly 1 in every 10,000 patients when utilizing graded talc. The second concern is obstruction of the tunneled pleural catheter by talc. This happens spontaneously in about 10% of patients and can be managed in >90% of these patients with the instillation of tissue plasminogen activator through the catheter. Previous trials of talc instillation through tunneled pleural catheters have not noted a higher than baseline rate of TPC blockage with this treatment regimen. Expected side effects of talc instillation include pain and fever which are temporary and can be treated with over the counter analgesics and anti-pyretics.

Potential benefits of participation in this study include less long-term fluid collection and potential earlier removal of the catheter.

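### Catheter obstruction is a named talc risk, but fibrin blockage is kept out of adverse events, talc blockage is unassigned, and no comparison by arm is planned

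*Combined protocol and SAP*

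**What the plan says.** Design and Procedures lists three secondary endpoints: quality of life, dyspnea and adverse events. Only the last is a harm endpoint. The study is described there as non-blinded.

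The risk/benefit assessment (under Subject Recruitment and Compensation) opens with "There are two primary risks to patients associated with this study". Respiratory failure comes first; then "The second concern is obstruction of the tunneled pleural catheter by talc". The next sentence reads "This happens spontaneously in about 10% of patients and can be managed in >90% of these patients", the management being a fibrinolytic given through the catheter. It adds that earlier trials "have not noted a higher than baseline rate of TPC blockage with this treatment regimen".

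The Adverse Events section reads "Anticipated adverse events include pain with drainage, catheter dislodgement, catheter malplacement, insertion site cellulitis, and empyema". Obstruction of any cause is not on that list. The section continues: "Catheter obstruction due to fibrin will be considered catheter failure, but not an adverse event".

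Management of Dysfunctional Catheters sends every obstructed catheter to a fibrinolytic and describes three outcomes. If drainage is restored, the patient goes back to the study protocol and no label is given. If it is not restored and there is no shortness of breath, "the catheter will be removed and the patient will be considered to have undergone partial response". If shortness of breath continues, the patient is a catheter failure.

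Follow-up Data Collection lists performance scores, the dyspnea scale, SF-36, chest x-ray scoring and an ultrasound at removal. Obstruction, fibrinolytic use and catheter failure are not listed. Data Analysis and Statistics plans no comparison of any of the three.

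**The concern.** An event that the protocol itself treats as a main hazard of the experimental treatment should appear in the planned comparison of harms. Here its place depends on the presumed cause. Fibrin blockage is expressly outside adverse events, and talc blockage is neither listed nor excluded. Only one arm receives talc, and the study is open-label, so the same clinical event can be labelled differently in the two arms. The category that receives fibrin blockage, catheter failure, has two definitions and no planned analysis.

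There is also a link to efficacy. A blocked catheter drains little, and low output is the drainage criterion for pleurodesis. Under Outcome Measures, having the catheter removed by day 30 achieves the primary endpoint, and responders are graded complete or partial. An uncleared blockage without dyspnea that leads to removal by day 30 is called a partial response and can therefore be counted as a success. The Adverse Events section would call the same patient a catheter failure if the blockage were fibrin.

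At stake is whether the report can say anything reliable about blockage with talc plus daily drainage.

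**Working it through.** **1. The sections side by side**

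| Event | Adverse Events section | Management of Dysfunctional Catheters |
|---|---|---|
| Fibrin blockage, cleared | Catheter failure, not an adverse event | Returns to protocol, no label |
| Fibrin blockage, uncleared, no dyspnea | Catheter failure, not an adverse event | Partial response |
| Fibrin blockage, uncleared, dyspnea continues | Catheter failure, not an adverse event | Catheter failure |
| Talc blockage | Not mentioned | Same three outcomes; cause plays no part |

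The two sections agree on only one of the three fibrin rows.

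**2. Inputs**
- Obstruction rate about 10%, with more than 90% of cases managed: risk/benefit assessment.
- 92 per group, 101 per arm with dropout: Power Calculation. These serve only as denominators here. The plan has no calculation on obstruction to reproduce. (The 92 does not itself follow from its stated inputs: the usual pooled one-sided formula for 45% against 65% at 90% power gives 105. That is a separate matter and changes nothing below.)
- Talc-arm obstruction rates of 15% to 30%: assumptions, not in the documents.

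**3. Expected counts at the protocol's rate**
- Obstructions per arm: 92 × 0.10 = 9.2; 101 × 0.10 = 10.1.
- Uncleared per arm, upper limit because more than 90% are managed: 9.2 × 0.10 = 0.92; 10.1 × 0.10 = 1.01.
- If only the narrower catheter-failure label were tabulated, at least 10.1 − 1.01 ≈ 9 of about 10 obstructions per arm would carry no label.
- Effect on the primary endpoint: at most 1.01 / 101 = 1.0 percentage point per arm, and less once cases with continued dyspnea are removed. At an assumed 20% talc-arm rate the limit in that arm is 101 × 0.20 × 0.10 = 2.0 patients. The design difference is 20 points.

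**4. What counting every obstruction would show**

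Precision if both arms are at 10%: the 95% half-width is 1.96 × √(2 × 0.10 × 0.90 / n), which is 8.7 points at n = 92 and 8.3 at n = 101.

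Power, with p₁ = 0.10, p₂ the assumed talc-arm rate and p̄ their mean:

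Φ{ [ (p₂ − p₁)√n − z·√(2p̄(1 − p̄)) ] / √(p₁(1 − p₁) + p₂(1 − p₂)) }

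For p₂ = 0.20, n = 101, two-sided 0.05: (1.005 − 1.96 × 0.505) / 0.5 = 0.03, giving 51%.

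| Assumed talc-arm rate | Extra events at n = 101 | Two-sided power, n = 101 | Two-sided power, n = 92 |
|---|---|---|---|
| 15% | 5.0 | 19% | 17% |
| 20% | 10.1 | 51% | 48% |
| 25% | 15.1 | 81% | 77% |
| 30% | 20.2 | 95% | 93% |

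The one-sided figure for 20% at 101 per arm is 64%. It is the more favourable version and should not be quoted alone.

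**The case against.** The strongest reply is that the exclusion is worded for fibrin only, while the named risk is blockage by talc. A reader might infer that the protocol bars the named risk from adverse events. It does not. Talc blockage could be reported, since the anticipated list is introduced as inclusive and adverse events are reviewed at baseline and every follow-up visit. This stands as a limit on the point. It does not remove it, because nothing in the documents says how to tell the causes apart, and the risk paragraph itself moves from blockage by talc straight to a spontaneous rate. Catheter work-up is referred to the earlier trial's protocol, which is not in these documents and might contain a rule.

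A reader might also infer that obstructions would be invisible and that the trial has no power to see an excess. That goes too far. Fibrin blockage is moved to another category, which could be tabulated by arm if recorded. The case report forms are not in the documents, so absence of capture is not shown. What is missing is a planned comparison and one definition.

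The plan reports no excess blockage in earlier trials. That is fair grounds for a low prior expectation. But the Background says that patients in the talc study drained every other day or by symptoms, so daily drainage with talc is not the same setting.

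Three further inferences are unsupported. Obstruction is listed second of the two risks and is not ranked as the leading one. No section says that every control-arm blockage is fibrin, or who attributes cause; that attribution can differ by arm is inferred from the open-label design. And the absence of respiratory failure and fever from the anticipated list does not stop them being reported, because the list is not exhaustive.

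**Conclusion.** The concern holds in this form: fibrin obstruction is outside the only harm endpoint, talc obstruction is unassigned, and the substitute category is defined in two ways and has no planned comparison by arm. This affects about 9 to 10 expected obstructions per arm at the protocol's 10% rate. The effect on the primary endpoint is real but small, with fewer than about 1 uncleared case per arm at the plan's rates.

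Counting every obstruction would not make the trial decisive on this risk. Two-sided power at 101 per arm is about 19%, 51%, 81% and 95% for assumed talc-arm rates of 15%, 20%, 25% and 30%. It would allow an estimate with an interval of about ±8 to 9 points if both arms are at 10%. The documents do not support the stronger conclusion that the trial cannot show an excess. The change should be made: the inconsistency concerns a named treatment risk and is cheap to repair.

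**What to change.** 1. Record every catheter obstruction and every fibrinolytic use in both arms, whatever the presumed cause, with date and outcome. Compare them by arm as a prespecified safety outcome, with a difference in proportions and a 95% interval. This replaces the exclusion of fibrin obstruction from the harm comparison.
2. Reconcile the Adverse Events section, Management of Dysfunctional Catheters and Outcome Measures, so that an uncleared obstruction is not a response in one place and a failure in another.
3. Report the primary endpoint with removals for uncleared obstruction counted as not achieved, at least as a sensitivity analysis.

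These are changes to recording, classification and analysis; catheter management is untouched. The cost is some wording, a form field and a somewhat higher count of harms. No extra visits or patients are needed.
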